4.2.3 Replacements

Subjects who discontinue prematurely from the study will not be replaced.

5 Study Treatments

Refer to Section 3.1 for a full description of the study design. All subjects will receive GTx-024 3 mg administered orally, once daily. Study drug will be supplied as opaque, white to off-white, size 5, oval softgel capsules.

5.1 Method of Assigning Subjects to Treatment Groups

Subjects who meet all eligibility criteria will continue the current open-label extension study with randomization code as assigned by an interactive web response system.

5.2 Treatments Administered

Study drug (Section 5) will be taken orally with water at approximately the same time each day, with or without food. Subjects will be required to take one 3 mg Softgel capsule per day. In the event of a missed dose, subjects will be instructed to skip the missed dose and continue dosing as per label instructions from the next day.

5.3 Identity of Study Drug

The GTx-024 study drug is an opaque, white to off-white, size 5, oval softgel capsule that contains the active ingredient GTx-024 (3 mg) dissolved in the inactive excipient polyethylene glycol 400. All study drug capsules will be imprinted with “GTx” in black ink on the outer shell of the capsule.

5.4 Management of Clinical Supplies

GTx, Inc. will provide adequate supplies of study drug through a central distribution center to clinical sites.

5.4.1 Study Drug Packaging and Storage

Study drug will be packaged in high-density polyethylene bottles with induction seal and child-resistant closure. Each bottle will contain sufficient study drug for 35 days of dosing according to the study protocol. Three bottles (a total of 105 dosing days) will be packaged together in one subject kit. For the first 3 visits, sites will collect the study drug previously dispensed, perform accountability, and re-dispense the same kit.

Each subject kit, and the bottles contained in the kit, will be labeled with a unique medication identification number. A clinical label with the medication identification number will be affixed to the outside of each bottle and subject kit. The label will also specify storage and dosing information.

At the study site, study drug must be stored in a secure area (e.g., a locked cabinet), protected from moisture, and kept at a controlled room temperature of 15°C to 25°C (59°F-77°F), with excursions permitted to 30°C (86°F).

5.4.2 Study Drug Accountability

The investigator will maintain accurate records of receipt of all study drug, including dates of receipt. In addition, accurate records will be kept regarding when and how much study drug is dispensed to and used by each subject in the study. Reasons for departure from the expected dispensing regimen must be recorded. At the completion of the study, to satisfy regulatory requirements regarding drug accountability, all study drug will be reconciled and retained or destroyed according to applicable regulations and Sponsor requirements.

5.5 Overdose Management

In Phase 1 studies, subjects have safely received single doses of up to GTx-024 100 mg. The likelihood of a need for other than symptomatic treatment of overdose is considered extremely low. In the event of an overdose reported to the study site, the medical monitor should be contacted immediately.

5.5.1 Medication Errors

Dispensing study drug to subjects for self-administration in an outpatient study increases the risk of medication errors. All errors in medication dispensing or administration must be carefully documented. These errors may include (but are not limited to) providing the wrong dose, medication loss, or administration at the wrong time of day. Adherence to the medication protocol will be emphasized at every visit.

5.5.2 Treatment of Medication Errors

The treatment of medication errors should be discussed with the medical monitor on a case-by-case basis.

5.6 Blinding

This is an open-label study, and all subjects will receive study drug (GTx-024 3 mg).

5.6.1 Breaking the Blind

Not applicable, as this is an open-label study.

5.7 Treatment Compliance

Individual subject compliance in taking study drug will be monitored by counting the unused medication that is returned by the subject at visits. Compliance will be documented. If compliance is < 80% or > 120%, the investigator or designee is to counsel the subject and ensure that steps are taken to improve compliance. Subjects who are < 80% or > 120% compliant with the dose regimen for any 2 consecutive visit periods during the study may be withdrawn from the study.

5.8 Prior and Concomitant Medications

The investigator or designee must record the use of prior medications (all medication taken within 30 days prior to baseline, Day 0) and current treatment (including both drug and nondrug therapies and all prescribed, over-the-counter [OTC], and alternative medicines) in the eCRFs. The minimum requirement is that the drug name and dates of administration are to be recorded. This also includes drugs used on a chronic or as-needed basis. Subjects must be instructed not to start any new medication, either prescribed or OTC, without consulting the investigator, unless the new medication is required for emergency use. Subjects must be instructed to notify the investigator immediately if medications are required for emergency use.

Any changes in concomitant medications also will be recorded in the subject's eCRF.

Any concomitant medication deemed necessary for the welfare of the subject during the study may be given at the discretion of the investigator. However, it is the responsibility of the investigator to ensure that details regarding the medication are recorded in full in the eCRF.

5.8.1 Prohibited Concomitant Medications and Treatments

Prohibited medications and treatments during the study duration include the following:

- Systemic hormonal products including, but not limited to, estrogens; progestins; testosterone; methyltestosterone; oxandrolone (Oxandrin[®]); oxymetholone; danazol; fluoxymesterone (Halotestin[®]); other androgenic compounds, including herbals such as fenugreek, Korean ginseng, goat weed, forskolin, and ashwagandha; and Testro-X[®]. Intravaginal application of estradiol topical/tablet agents and hormones delivered via vaginal ring are allowed

- Any new treatment (medication or otherwise), including vaginal rejuvenation, that is known or suspected to affect lower urinary tract function throughout the treatment and follow-up periods
- Treatment with any other investigational agent
- New pelvic floor exercises (including Kegel) throughout the follow-up period

6 Study Assessments and Procedures

Before performing any study procedures, all potential subjects will sign an additional informed consent form (ICF) for this open-label extension study. Subjects will have the opportunity to have any questions answered before they sign the ICF. The investigator must address all questions raised by the subject. The investigator will also sign the ICF.

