4.1.2 Exclusion Criteria

A subject who meets any of the following criteria will be excluded from the study:

1. Starts any new treatment (medication, pelvic floor physical therapy, or other treatment known to impact the pelvic floor) after completing G201002 that is known or suspected to affect lower urinary tract function, including vaginal rejuvenation
2. Subject is currently taking systemic sex-hormone products (excludes intravaginal application of estradiol topical/tablet agents and hormones delivered via vaginal rings). The following washout periods are required if systemic hormonal products are discontinued prior to screening:
 - a. minimum of 4 weeks for prior transdermal products or products with systemic absorption applied topically;
 - b. minimum of 8 weeks for prior oral products;
 - c. minimum of 8 weeks for prior intrauterine products, and;
 - d. minimum of 3 months for prior hormonal implants or injectable drug therapy.
3. Has a current cancer diagnosis (with the exception of nonmelanoma skin cancer) or any history of breast or endometrial cancer
4. Has a known history or current episode of:
 - a. New York Heart Association Stage ≥ 2 hypertension (systolic blood pressure > 160 mmHg or diastolic blood pressure > 100 mmHg) at screening and/or baseline. Subjects with hypertension that has been treated and controlled with medication for ≥ 2 weeks prior to screening are eligible for participation
 - b. Recent myocardial infarction or arterial or venous thromboembolic event (within 1 year) or a history of more than 1 myocardial infarction or arterial or venous thromboembolic event
 - c. Cardiac-related syncopal event within the past year

- d. Cardio or cerebral vascular disease requiring surgical intervention (e.g., bypass surgery, angioplasty). For subjects with previous stent placement, please contact the medical monitor
- e. Congestive heart failure of Stage > 2 according to New York Heart Association criteria
- f. Angina pectoris

5. Has a current or past history of any physical condition that, in the investigator's opinion, might put the subject at risk, impact absorption of the study drug, or interfere with interpretation of study results

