6.3.1.2 Eliciting and Documenting Adverse Events

Adverse events will be assessed beginning at enrollment (date of signed informed consent) through the end of the study.

Serious AEs that occur more than 30 days after the last dose of study drug need not be reported unless the investigator considers them to be related to study drug.

At every study visit, subjects will be asked a standard nonleading question to elicit any medically related changes in their well-being. They will also be asked if they have been hospitalized, had any accidents, used any new medications, or changed concomitant medication regimens (both prescription and OTC medications).

In addition to subject observations, AEs identified from any study data (e.g., laboratory values, physical examination findings) or identified from review of other documents (e.g., subject diaries) that are relevant to subject safety will be documented on the AE page in the eCRF.

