6.3.3.3 Prior and Concomitant Medications

At the baseline visit, the investigator or designee must record the use of prescription and OTC medication taken within the prior 30 days. Concomitant medications (including prescription and OTC medications) will be assessed and recorded throughout the study (Table 12–1).

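### The bullet on new pelvic floor exercises in 5.8.1 names only the follow-up period, which conflicts with the rest of the list, and no visit question prompts disclosure of nondrug therapy; the impact is minor

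*Combined protocol and SAP*

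**What the plan says.** Section 5.8.1 opens with "Prohibited medications and treatments during the study duration include the following". Its second bullet covers any new treatment, drug or not, that is "known or suspected to affect lower urinary tract function throughout the treatment and follow-up periods". Its last bullet, the only one to name pelvic floor exercises, reads "New pelvic floor exercises (including Kegel) throughout the follow-up period".

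On recording, section 5.8 requires "current treatment (including both drug and nondrug therapies" and all medicines) to be entered in the eCRF. Its later sentence is narrower: "Any changes in concomitant medications also will be recorded in the" eCRF. At every visit, section 6.3.1.2 has staff ask an open question about well-being. They also ask whether the woman has been hospitalized, had an accident, or "used any new medications, or changed concomitant medication regimens". Section 6.3.3.3 says "Concomitant medications (including prescription and OTC medications) will be assessed and recorded throughout the study", and Table 12-1 has a matching row for concomitant medications.

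Exclusion 1 in section 4.1.2 bars women who have begun new treatment since G201002 that may affect the lower urinary tract. It names pelvic floor physical therapy and adds "or other treatment known to impact the pelvic floor". Table 12-1 schedules the eligibility review at baseline only.

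**The concern.** One short list gives different time spans for what is arguably the same prohibition, and the span attached to the specific item is the shortest. A rule that names the item tends to be followed over a general one, so a coordinator checking whether a woman on GTx-024 may begin Kegel exercises could conclude that she may. With about 65 sites, some are likely to read it differently from others.

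All five secondary endpoints could be affected: the stress, urge and total leak counts, and the PGI-S and PGI-I. Every subject receives GTx-024 3 mg and there is no control arm. Any benefit from exercises begun on treatment would therefore appear in the by-visit summaries as improvement on the drug. The PGI-I invites this directly, because it asks for a comparison with the time before study medication began. If the start is never mentioned at a visit, nobody can say how many women it concerns.

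**Working it through.** The plan gives no figure on this point, so the check is mainly a comparison of texts.

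**1. Time spans within 5.8.1**

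| Text | Period covered | New exercises on drug |
|---|---|---|
| Lead-in | Study duration; section 4.2 runs this for each subject from consent to the last follow-up visit | Barred |
| Second bullet | Treatment and follow-up | Barred, if exercise counts as a new treatment |
| Last bullet | Follow-up only | Not mentioned |

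The second bullet names treatment and follow-up as two separate periods. The last bullet, which names one of them, is therefore hard to read as covering both.

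**2. What the follow-up period could be.** The only period of that name with a stated length is the 4-week one in G201002 (section 1.1). The nearest equivalent here is the interval from the last dose to the end-of-study visit about 30 days later (section 6.1.4, Table 12-1). Treatment has no planned end (section 3.1). Taken literally, the last bullet covers roughly a month off drug and leaves out the whole on-drug period from which efficacy is summarized.

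**3. What would bring a start to light**

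- Section 6.3.1.2 has four specific questions: hospitalization, accidents, new medications, changed medication regimens. Two concern treatment, and 0 of those 2 cover nondrug therapy.
- Table 12-1 has 18 procedure rows. One concerns other treatments, and it is limited to medications, so 0 of 18 name nondrug therapy. These are row labels and the eCRF is not among the documents. The count shows that no prompt is scheduled, not that no field exists.
- Section 5.8 does require nondrug therapies to be recorded. However, its minimum content is drug name and dates, its instruction to subjects is about new medication, and its sentence on changes is about medications.

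**4. Size.** Let *r* be the share of women in a by-visit summary who began exercises on drug, and *d* their mean gain from the exercises in leaks per day. Because all collected data are used (section 4.2.2), the mean reduction on drug is overstated by *r* × *d*. The documents give neither quantity. Assumed values, for scale only:

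- *r* = 2%, *d* = 0.5: 0.02 × 0.5 = 0.01 leaks/day
- *r* = 5%, *d* = 1: 0.05 × 1 = 0.05 leaks/day
- *r* = 10%, *d* = 2: 0.10 × 2 = 0.20 leaks/day

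At the enrollment ceiling of 500, those shares are 10, 25 and 50 women. The range reflects the assumptions and is not an estimate.

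**The case against.** The strongest reply is that new exercises on drug are already prohibited. The lead-in covers the study, the second bullet covers treatments of any kind in both periods, and Exclusion 1 shows that the sponsor counts pelvic floor physical therapy among them. Section 3.1 also has visits attended by subjects who continue to meet the eligibility criteria, which supports a continuing restriction even though no repeat check is scheduled. This stands as the better reading of the protocol. It does not remove the conflict, because a site must set the specific bullet aside to reach it.

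The second reply is that starts can be recorded and reported. Section 10.2.2 requires any deviation to be explained in the source documents and documented by the monitor. Section 4.2.1 commits the clinical study report to details of breaches of the study's prohibitions. Section 5.8 covers nondrug therapy. This also stands, but only for starts that someone learns about. None of these provisions prompts the woman to say so, and a site that reads the bullet as permission would not log a deviation.

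The third reply is that little depends on efficacy here. It is secondary and descriptive, with no formal testing and no power calculation (sections 7.3 and 7.6). That is correct, and it sets the grade of the point.

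**Conclusion.** The conflict in 5.8.1 is real, and no scheduled visit question prompts disclosure of nondrug therapy. The impact is minor. It is confined to descriptive, single-arm secondary efficacy, its size cannot be estimated from the documents, and the primary safety objective is unaffected.

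A reader might infer three stronger things, and the documents support none of them:

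- **That the protocol allows new Kegel exercises on drug.** It does not clearly do so. The lead-in and second bullet point the other way, and the fault is an ambiguity.
- **That such starts would go unrecorded and could never be reported.** A known start is a deviation with its own documentation and reporting duties. The gap is in eliciting it.
- **That secondary efficacy is biased by a known or large amount.** The arithmetic above multiplies two assumed numbers, and the documents contain no rate of new exercise and no effect of exercise.

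The conclusion rests on two judgments: that some sites would follow the specific bullet over the general text, and that women would not reliably volunteer an exercise start in answer to an open well-being question.

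**What to change.** 1. In the last bullet of 5.8.1, insert the words *treatment and* before *follow-up* and make *period* plural, so that its span matches the second bullet. With treatment named, the lack of a defined follow-up period matters much less.
2. In 6.3.1.2, extend the visit questions to new nondrug pelvic floor treatment (exercises, physical therapy, procedures). Record the start date under the existing duty in 5.8 to record nondrug therapies.
3. Optional: beside the unchanged all-data summary at each visit, show the number of women who have begun such treatment by then. Section 4.2.1 already requires breaches of the prohibitions to be reported, so this is a convenience for the reader. No subject is excluded and nothing is imputed.

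The cost is one wording edit, one added visit question and a start date in the eCRF, plus one count line per visit if the optional item is taken up. The downside is a few more deviations for sites to manage.

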6.1 Study Visits

The schedule of events for this study is presented in Table 12–1.

6.1.1 Baseline (Day 0)

The study will be explained in detail, and adequate time will be allowed for answering questions from a potential subject before she signs the institutional review board (IRB)–approved informed consent document. Informed consent will be obtained from those potential subjects who meet initial inclusion/exclusion criteria and express willingness to participate before study site personnel conduct any study assessments of such subjects.

Once informed consent is obtained, the subjects will be assigned a subject number and a detailed interview will be conducted with the subject about her concomitant medications, and recent medical history will be evaluated. Height and weight will be measured, and vital signs will be assessed as presented in Table 12–1.

The subject’s eligibility criteria will be reviewed. During the visit, the subject will complete the PGI-S. Blood will be drawn for a comprehensive metabolic panel (CMP), complete blood count (CBC), lipid panel, hormone panel, and SHBG tests. A baseline transvaginal ultrasound examination will also be performed in subjects with an intact uterus.

The subject will be provided with a 3-day voiding diary and instructed to complete the 3-day voiding diary within the week preceding her next study visit.

Study drug will be dispensed with administration instructions. The medication identification number assigned to the subject will be noted in the eCRF for study drug accountability. The subject will take the first dose of study drug during the baseline visit. The subject will be reminded to bring all unused study drug (in its original packaging) to her next clinic visit. Any subject who prematurely discontinues the study or study drug will be asked to return to the study site and complete end-of-study assessments.

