3.1.1.1 Risk Mitigation

This study has been designed to mitigate known risks associated with the use of GTx-024. Clinical study G200501 observed the effects of administering doses of 0.1, 0.3, 1, and 3 mg of GTx-024 (or placebo) for 86 days to healthy subjects: postmenopausal women and elderly men. Dose-dependent increases in serum alanine aminotransferase (ALT) and aspartate aminotransferase (AST) were observed. A higher incidence of transient, asymptomatic increases in ALT levels reported as AEs occurred in the group receiving GTx-024 3 mg (20.8%) compared with the placebo group (0%). One subject who received 3 mg/day of GTx-024 was discontinued due to an ALT level >3 times the upper limit of normal (ULN). The ALT levels returned to normal with continued exposure to GTx-024 in most cases and, furthermore, in instances when dosing was not continued, levels returned to normal. No significant increases in levels of total bilirubin, gamma glutamyl transferase, alkaline phosphatase, or lactate dehydrogenase have been observed in subjects with elevated ALT levels. Consistent with the effects of other orally administered anabolic agents, GTx-024 causes a dose-dependent reduction in high-density lipoprotein (HDL), the clinical significance of which is unknown at this time. The proposed mechanism for reduction in HDL is due to stimulation of reverse cholesterol transport and increased HDL catabolism by hepatic lipase. Reductions in HDL levels are temporary and typically return to baseline levels 12 months after treatment initiation.

In an ongoing, Phase 2 study of GTx-024 in estrogen receptor-positive/androgen receptor-positive breast cancer that is examining daily doses of GTx-024 at 9 and 18 mg, several cases of clinically significant hypercalcemia have been observed that were assessed by the investigators as possibly related to GTx-024. Subjects with hypercalcemia had

estrogen receptor–positive breast cancer with bone metastases. Hypercalcemia has not been observed in previous studies of healthy individuals or at doses <9 mg.

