Subjects will be monitored at each visit for health changes since the previous visit and adverse effects of treatment. Since elevations in ALT levels have been observed in prior studies, serum ALT and other liver function analytes will be monitored at each visit during treatment (Table 12–1). Stopping rules have been included for severe elevations of liver function tests or other signs of hepatotoxicity (Section 6.3.2). Subjects will also be monitored for changes in lipid profile and serum calcium.

The effect of GTx-024 on a fetus has not been evaluated; therefore, the subjects in the current investigation will be postmenopausal.

4 Subject Selection and Withdrawal Criteria

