4.1 Selection of Study Population

Up to 500 subjects will be enrolled at around 65 sites in the United States (US). Subjects will be enrolled in the current study only if they meet all of the inclusion criteria and none of the exclusion criteria.

Deviations from the inclusion and exclusion criteria are not allowed because they can potentially jeopardize the scientific integrity of the study, regulatory acceptability, or subject safety. Therefore, adherence to the criteria as specified in the protocol is essential.

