4.1.1 Inclusion Criteria

Each subject must meet all of the following criteria to be enrolled in this study:

1. Be an eligible subject from G201002, where an eligible subject is defined as:
 - a. one of the first 225 subjects who were randomly assigned to the placebo group in G201002 and who have completed the required treatment and durability periods of that study, or;
 - b. any subject from 226 onwards, who was randomly assigned to any treatment group and who completed the required treatment and follow-up periods of that study
2. Be able to read, understand, and provide written, dated informed consent prior to enrollment in the current study and be likely to comply with the study protocol and communicate with study personnel about AEs and other clinically important information
3. Provide written consent to participate in the study within the following timeframes:
 - a. for G201002 Subjects 1-225, within 30 days after the unblinding of G201002 (subjects who consent to participate in G201003 will be allowed to discontinue from that study and consent to this study upon unblinding of G201002)
 - b. for G201002 Subjects 226-493, within 30 days of completing both the treatment and follow-up period of G201002

4. Agree to maintain a stable dose of any medication known to affect lower urinary tract function, including but not limited to anticholinergics, tricyclic antidepressants, beta-3 adrenergic agonists, or α -adrenergic blockers, throughout the duration of the study

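### No liver value has to be seen before the first dose: the protocol sets no ALT, AST or bilirubin entry limit, and the baseline panel is drawn at the visit where dosing starts

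*Combined protocol and SAP*

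**What the plan says.** **Order of events on Day 0.** Protocol section 6.1.1 puts consent, medical history, eligibility review, blood sampling, dispensing and first dose in one visit. On sampling it says: "Blood will be drawn for a comprehensive metabolic panel (CMP), complete blood count (CBC), lipid panel, hormone panel, and SHBG tests". Section 6.6 shows that the metabolic panel contains ALT, AST and bilirubin. On dosing, 6.1.1 says: "The subject will take the first dose of study drug during the baseline visit". Table 12-1 agrees and has no earlier visit, although section 4.1.2 refers to screening.

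**Entry criteria.** None of the four inclusion criteria (4.1.1) or five exclusion criteria (4.1.2) names a liver test. The route in is through G201002. Criterion 1a admits a woman who is "one of the first 225 subjects who were randomly assigned to the placebo group in G201002" and who finished the treatment and durability periods. Criterion 1b admits anyone from Subject 226 onwards "who completed the required treatment and follow-up periods of that study".

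**Risk and mitigation.** Section 3.1.1.1 reports dose-dependent ALT and AST increases. In G200501, ALT rises recorded as adverse events occurred in 20.8% on 3 mg and 0% on placebo. The stated mitigation is that "serum ALT and other liver function analytes will be monitored at each visit during treatment", together with the stopping rules in 6.3.2.

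**Stopping rules.** Section 6.3.2 asks for discontinuation to be considered in any of these cases:
- ALT or AST > 8 x ULN;
- ALT or AST > 5 x ULN for more than 2 weeks;
- ALT or AST > 3 x ULN with total bilirubin > 2 x ULN or INR > 1.5;
- ALT or AST > 3 x ULN with listed symptoms or eosinophilia.

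Any ALT or AST > 3 x ULN brings the subject back for an unscheduled visit and an INR.

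**The concern.** Both mitigations for the named liver risk act only after exposure has begun. Exclusion 4a sets a measured entry limit for blood pressure, but the laboratory risk that the protocol itself singles out has none. As a result, the entry rule can admit a woman whom the stopping rule would at once consider taking off treatment. An asymptomatic raised value is exactly what history-taking does not find.

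What is at stake is the safety of individual women, not the estimates. The panel is described ahead of the first dose, so a raised value would be recorded as a baseline value and would enter the shift tables as such.

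**Working it through.** The protocol states no figure to reproduce. The check is mainly a reading of each provision that might put a liver value in front of someone before dosing, or stop dosing afterwards.

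**Before the first dose**

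| Provision | What it does | Requires a liver value to be seen? |
|---|---|---|
| 4.1.1, criteria 1a and 1b | Admits only women who completed the required G201002 periods | No |
| 4.1.2, exclusion 5 | Excludes for a physical condition the investigator thinks risky | No; the condition must be known |
| 6.1.1, medical history and medication interview | May reveal known liver disease or a hepatotoxic drug | No |
| 6.1.1, eligibility review | Applies 4.1.1 and 4.1.2 | No; neither contains a liver limit |
| 6.1.1, metabolic panel | Measures ALT, AST and bilirubin | Drawn, but the result need not be back |

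For Subjects 1-225 only placebo women enter, so completing G201002 says nothing about how they tolerate the drug. Their consent window runs from unblinding, so the age of their last G201002 value has no stated upper limit.

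**After the first dose**

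| Provision | What it does | States that dosing pauses? |
|---|---|---|
| 6.6 | Clinically significant abnormal results are recorded as adverse events; the investigator may repeat the panel | No |
| 6.3.1.6 | Adverse events are followed until resolved or stable | No |
| 6.3.2, opening paragraph, and 4.2.1 | The investigator, with the medical monitor or sponsor, may discontinue a subject at any level | Only by judgement |
| 6.3.2, listed multiples | Discontinuation to be considered | Only by judgement |
| 6.3.2, > 3 x ULN | Recall visit and INR | No; no timing is given |

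Two of the 6.3.2 criteria can be met on the Day 0 panel alone: ALT or AST > 8 x ULN, and ALT or AST > 3 x ULN with total bilirubin > 2 x ULN. Neither bars entry.

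**Length of exposure.** If dosing stops on day *t* after one dose a day from Day 0, *t* doses have been taken. The documents give no turnaround or recall time. For an assumed *t* of 1 to 7 days, that is 1 to 7 doses, or 3 to 21 mg (7 x 3 = 21).

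**How many women.** Section 4.1 says "Up to 500 subjects will be enrolled at around 65 sites", but the criteria allow fewer:
- Subjects 226-493: 493 - 226 + 1 = 268.
- Placebo women among the first 225: the allocation is not given. At an assumed one-third to one-half, 225/3 = 75 to 225/2, about 112.
- Ceiling before dropout: 268 + 75 = 343 to 268 + 112 = 380.

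The share with ALT or AST > 3 x ULN on Day 0 is not in the documents. An assumed 0.1% to 1% gives 343 x 0.001 = 0.34 to 380 x 0.01 = 3.8 women. The chance of at least one is 1 - 0.999^343 = 0.29 to 1 - 0.99^380 = 0.98. That range reflects the assumed rates and nothing else. It shows why no frequency should be claimed.

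**The case against.** The strongest case against runs as follows. This is a rollover study in women who passed a 4-week screening period in G201002 and completed it. The tolerability record in the protocol is mostly reassuring: "The ALT levels returned to normal with continued exposure to GTx-024 in most cases", no significant bilirubin rise was seen in subjects with raised ALT, and single doses up to 100 mg were generally well tolerated (3.1.1). A woman found with a raised Day 0 value will have had a few 3 mg doses and can be recalled, retested and withdrawn.

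Most of this stands as a limit on size. It does not close the gap. The liver criteria and laboratory schedule of G201002 are not in these documents, and this protocol does not ask anyone to consult its results. The ALT reassurance concerns rises that appeared on drug, not women who start with a raised value. One person on 3 mg in G200501 was taken off treatment for ALT above 3 x ULN.

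A reader might also infer three stronger points, which the documents do not support:
- **That treatment can be stopped only at the listed multiples.** The opening paragraph of 6.3.2, and 4.2.1, allow discontinuation at any level on the investigator's judgement.
- **That a raised Day 0 value goes unattended until the Week 4 panel (Day 21 to 35).** Above 3 x ULN, section 6.3.2 requires a recall visit, so the relevant interval is turnaround plus recall time.
- **That every first dose must wait for the Day 0 result.** That would remove the exposure entirely, but at the price of delaying every entrant. The documents show no harm from a few doses that would compel it.

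**Conclusion.** The gap is real and small. No liver value has to be seen before dosing with a drug whose named risk is ALT and AST elevation, and a woman already meeting a 6.3.2 liver criterion could be enrolled and dosed. The partial safeguards narrow the gap, but they neither require a pre-dose value nor say that dosing pauses.

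The conclusion rests on the text alone. It does not depend on the assumed prevalence, placebo share or turnaround time, none of which the documents supply. It would weaken if G201002 drew a late liver panel that sites review as a matter of course, but this protocol does not require that. The change is recommended because it is cheap and specific, not because harm has been shown.

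**What to change.** **(a) Entry limit and pre-dispensing check.** In 4.1.2, exclude a woman whose most recent available ALT or AST is > 3 x ULN, or total bilirubin > 2 x ULN, unless a repeat before dosing is below the limit. In 6.1.1, require the last available G201002 value to be checked at the eligibility review, before dispensing. These levels already appear in 6.3.2. Used singly at entry they are stricter than 6.3.2 is for a woman on treatment, and the sponsor may prefer others.

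**(b) Day 0 review.** Require the Day 0 panel to be reviewed on receipt, and dosing to be interrupted pending a repeat if it exceeds the same limit.

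**Cost.** A short amendment, one check, one review step, and a few women delayed or not entered.

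**What remains.** A woman whose earlier value was normal, or who has none, can still take doses until her Day 0 result is acted on. Holding the first dose where no recent value exists would close most of that. It is optional, for the sponsor to weigh: depending on what G201002 collected, it could delay few women or all of them.
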